Three longitudinal biomarker substudies will evaluate the effects of study treatment on the underlying pathophysiology of AD using amyloid PET and/or CSF biomarkers. Participation in the substudies is optional and will require specific consent that will not affect enrollment or treatment in the main study. The tau PET substudy will be offered to study-eligible subjects from select geographical sites (based on proximity to the tau PET ligand manufacturing sites) in the US who have an amyloid positive study-specific PET scan and who have also consented to participate in the amyloid PET substudy. Tau PET scanning will be performed using a sponsor-supplied tau PET imaging agent, eg PI-2620. (revised per Amendments 04 and 05)

The maximum estimated duration for each subject in the Core Study is approximately 29 months (ie, 2-month Prerandomization Phase, followed by 24 months of blinded treatment in the Randomization Phase, and a 3-month follow-up).

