Eligible subjects may enter the Extension Phase immediately following the completion of Visit 15 of the Core Study. Subjects who are eligible to participate in the Extension Phase but who do not transition to the Extension Phase on the day of Visit 15 may enter the Extension Phase any time within 4 weeks of Visit 15. All subjects who enter the Extension Phase will be treated with elenbecestat, including the subjects who received placebo during the Core Study. For all subjects, assessments performed at Visit 15 will serve as baseline values for the Extension Phase. (revised per Amendment 05)

An independent data safety monitoring board (DSMB) will convene at regular intervals to monitor the overall safety of the study and to make recommendations to the sponsor related

to study safety as appropriate. The DSMB will be asked to review the cumulative safety data, which includes measures of cognitive safety at the group level, up to the date identified to make a determination if the trial is safe to proceed unchanged or to provide recommendations to the sponsor as to how to proceed. (revised per Amendment 05) The study will proceed, including randomization of additional subjects, during DSMB safety reviews. Details will be provided in the DSMB Charter.

An overview of the study design is presented in [Figure 1](#).

[figure not shown]

Figure 1 Study Design for E2609-G000-302 (revised per Amendment 05)

Elenbecestat = Test drug, EoT = End of Treatment, PET = positron emission tomography, R = randomization.

- a: Subjects who participate in the optional longitudinal tau PET substudy will be permitted an additional window of up to 5 days (resulting in a total of up to 85 days) in order to accommodate the additional tau PET scan required to be performed during prerandomization. (revised per Amendment 04)
- b: The last day of the Core Study (Visit 15) is also the first day of the Extension Phase

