9.7.1.8.1 EXTENT OF EXPOSURE

The Duration of exposure to study drug will be summarized as cumulative extent of exposure in categories with 3-month increment. The cumulative number and percent of subjects in each applicable exposure category will be presented by treatment group. Duration of exposure will be summarized using descriptive statistics as well as by 3-month duration categories using counts. The number and percent of subjects within each duration category will be presented by treatment group. Overall exposure (number of subject-months) is defined as summation over all subjects' exposure durations and will be summarized by treatment group.

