9.7.1.8.2 ADVERSE EVENTS

The AE verbatim descriptions (investigator terms from the eCRF) will be classified into standardized medical terminology using the Medical Dictionary for Regulatory Activities (MedDRA). AEs will be coded to the MedDRA (Version 19.0 or higher) lower level term closest to the verbatim term. The linked MedDRA PT and primary system organ class (SOC) are also captured in the database.

A TEAE is defined as:

- An AE that emerges on or after start of study treatment, having been absent at pretreatment (Baseline) or
- Reemerges on or after start of study treatment, having been present at pretreatment (Baseline) but stopped before treatment, or
- Worsens in severity on or after start of study treatment relative to the pretreatment state, when the AE is continuous. (revised per Amendment 03)

Only those AEs that are treatment-emergent will be included in summary tables. All AEs, treatment-emergent or otherwise, will be presented in subject data listings.

The TEAEs will be summarized by treatment group on the Safety Analysis Set. The incidence of TEAEs will be reported as the number (percentage) of subjects with TEAEs by SOC and PT. A subject will be counted only once within an SOC and PT, even if the subject experienced more than 1 TEAE within a specific SOC and PT. The number (percentage) of subjects with TEAEs will also be summarized by maximum severity (mild, moderate, or severe). The number (percentage) of subjects with TEAEs will also be summarized by relationship to study drug (Yes [related] and No [not related]).

The number (percentage) of subjects with treatment-related TEAEs will be summarized by SOC and PT. Treatment-related TEAEs include those events considered by the investigator to be related to study drug. The number (percentage) of subjects with treatment-related TEAEs will also be summarized by maximum severity (mild, moderate, or severe).

AEs will be summarized by the following subgroups: region, prior treatment with AChEIs or memantine (no or yes), and clinical subpopulation (MCI due to AD or the early stages of AD).

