1. Subjects who complete the 24-month Treatment Period and the 3-month Follow-up period (Visit 15) of the Core Study and whose Visit 15 falls within a 4-week window from the start of the Extension Phase. Subjects who discontinue study drug early are not considered to have ‘completed’ the Core Study.
2. Provide written informed consent. Subjects must, in the investigator’s judgment, have the capacity to consent (capacity to consent should be determined in accordance with applicable professional standards and local laws/regulations). In Japan, if a subject loses the capacity to consent, in the investigator's opinion during the course of the Core Study, the subject's assent should be obtained (if required in accordance with local laws, regulations, and customs) along with the written informed consent of a legal representative. (revised per Amendment 06)
3. Subjects must continue to have an identified study partner who is willing and able to provide follow-up information on the subject throughout the course of the Extension Phase.

Study Design and Plan

The Extension Phase allows eligible subjects to receive elenbecestat 50 mg for up to 24 months (2 years), or until commercial availability of elenbecestat or a lack of positive benefit-risk is determined, whichever comes first.

Subjects who are enrolled and complete the Core Study, including the 3-month follow-up period, will have the option to participate in the Extension Phase. Subjects who discontinue from study drug during the Core Study are not eligible to participate in the Extension Phase.

Eligible subjects may enter the Extension Phase immediately following the completion of Core Study Visit 15. Subjects who are eligible to participate in the Extension Phase but who do not transition to the Extension Phase on the day of Visit 15 may enter the Extension Phase any time within 4 weeks of Visit 15. For all subjects, assessments performed at Visit 15 may serve as baseline values for the Extension Phase.

Subjects may discontinue from the open-label study drug for any reason but are required to complete the Early Discontinuation (ED) Visit (within 7 days of last dose). In addition, subjects are required to discontinue the open-label study drug if any of the criteria specified in [Section 9.3.3](#) (Removal of Subjects from Therapy or Assessment) are met.

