Safety analysis will be performed similarly to analyses in the Core Study. The Core Study baseline will be used for subjects who are randomized to elenbecestat initially, the Extension Phase baseline will be used for subjects who are randomized to placebo but receive elenbecestat during the Extension Phase. The incidence of AEs (including changes from baseline in physical and neurological examinations, and dermatological assessments), out-of-normal-range laboratory safety test variables, abnormal ECG findings, out-of-range vital signs, suicidality (C-SSRS), and changes from baseline in laboratory safety test variables, ECGs, safety MRI, vital sign measurements will be summarized by using descriptive statistics.

Efficacy Analyses

The following efficacy endpoints will be summarized by descriptive statistics and graphs:

- Changes from baseline in CDR-SB, ADCOMS, MMSE, FAQ, ADAS-cog14, and ADAS-cog14 Word List (immediate recall and delayed recall)
- Time to conversion to dementia for subjects who were not clinically staged as dementia based on clinical diagnosis at Core Study baseline based on clinical diagnosis
- Change from baseline in NPI-10 and NPI-12
- Proportion of subjects who receive increase and/or initiation of other AD pharmacotherapies

A delayed-start analysis ([Liu-Seifert et al, 2015](#)) will be performed for each efficacy endpoint at various scheduled visits in the Extension Phase. In addition, a mixed effects model for repeated measures (MMRM) will be used to analyze the above endpoints where appropriate.

Biomarker Analyses

The following biomarker endpoints will be summarized by descriptive statistics and graphs:

- Change from baseline in amyloid PET standardized uptake value ratio (SUVR)
- Change from baseline in tau PET signal
- Change from baseline in total hippocampal volume as measured by vMRI
- Change from baseline in the preservation of connectivity as measured by fMRI

- Change from baseline in t-tau, p-tau, A β (1-42) and A β (1-x) in CSF
- Change from baseline A β (1-x) in plasma
- Change from baseline in exploratory biomarkers eg, NFL, VILIP1, YKL-40, and Ng in CSF and plasma

A delayed-start analysis and MMRM model will be used to analyze these biomarker endpoints.

The relationship between efficacy endpoints and biomarker endpoints will be explored using correlation analysis.

Sample Size Rationale

Not applicable.

Table 9 Schedule of Procedures/Assessments in Extension Phase

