19. Have participated in a clinical study involving:
- any therapeutic monoclonal antibody, protein derived from a monoclonal antibody, immunoglobulin therapy, or vaccine within 6 months before Screening for whom it cannot be documented that they were randomized only to placebo or never received study drug
 - elenbecestat
 - any new chemical entity or investigational drug for AD with last study drug dose occurring within 6 months before Screening unless it can be documented that the subject received only placebo (revised per Amendment 05)
 - any other investigational medication (unless it can be documented that the subject received only placebo) or device within 8 weeks or 5 half-lives (whichever is longer) before randomization
20. Planned surgery that requires general, spinal, or epidural anesthesia that would take place during

the study. Planned surgery which requires only local anesthesia and which can be undertaken as day case without inpatient stay postoperatively need not result in exclusion if in the opinion of the investigator this operation does not interfere with study procedures and subject safety.

Study Treatments

Core Study

Elenbecestat will be supplied by the sponsor as tablets of 50-mg dose strength in bottles of 35 tablets each. Placebo tablets to match elenbecestat will be of identical appearance. Each subject will receive 1 tablet of 50 mg elenbecestat or an identical placebo tablet, to be administered orally QD in the morning with or without food.

Extension Phase

Elenbecestat will be supplied by the sponsor as tablets of 50-mg dose strength in bottles of 35 tablets. Each subject will receive 1 tablet of 50 mg elenbecestat, to be administered orally QD in the morning with or without food. (revised per Amendment 05)

Duration of Treatment

Core Study: The maximum estimated duration for each subject is approximately 29 months (ie, 2-month Prerandomization Phase, followed by 24 months of blinded treatment in the Randomization Phase and a 3-month follow-up).

Extension Phase: The estimated duration for a subject is 25 months (ie, 24 months of treatment and 1-month follow-up). (revised per Amendment 05).

Concomitant Drug/Therapy (both Core Study and Extension Phase) The following agents are not permitted before randomization (specific time frames are shown below) and until the last visit during the Treatment Period: (revised per Amendment 01)

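### Extension Phase safety is summarised as crude percentages over AE windows of about 50 months (early start) and 25 months (delayed start), so the incidences can be neither compared nor pooled

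*Protocol*

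**What the plan says.** Protocol Appendix 5 (Safety Analyses), repeated in the synopsis, says that Extension safety follows the Core Study's approach and then sets the baseline by original arm: "The Core Study baseline will be used for subjects who are randomized to elenbecestat initially, the Extension Phase baseline will be used for subjects" randomised to placebo who are treated with elenbecestat in the Extension. Incidences of AEs, out-of-range laboratory values and vital signs, abnormal ECGs and suicidality, together with changes from baseline, are to be described. No between-group test is planned.

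The Core method is in section 9.7.1.8.2: "The TEAEs will be summarized by treatment group on the Safety Analysis Set", as number and percentage of subjects, each counted once per term. A TEAE there is an event that appears, returns or worsens after treatment starts, relative to the pretreatment state. Section 9.7.1.8.3 defines a markedly abnormal laboratory value through any postbaseline rise to a given grade. Section 9.7.1.8.1 plans a total of time on drug ("Overall exposure (number of subject-months) is defined as summation over all" subjects' durations), but no section uses it as a denominator for incidence.

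On durations, section 9.1 describes the Core Study as "followed by 24 months of blinded treatment in the Randomization Phase, and a 3-month follow-up", and the synopsis says of the Extension: "The estimated duration for a subject is 25 months (ie, 24 months of treatment and 1-month follow-up". Subjects who do not move over on the day of Visit 15 "may enter the Extension Phase any time within 4 weeks of Visit 15". In each phase new AEs are collected until 4 weeks after the last dose (section 9.3.3; notes to Table 9).

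On the population, Appendix 5 states: "Subjects who discontinue from study drug during the Core Study are not eligible to participate in the Extension Phase". The same appendix applies the Core analysis sets to the Extension, and section 9.7.1.2 admits to the Safety Analysis Set anyone with one dose and one postdose safety assessment.

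**The concern.** The chance that a subject has at least one event, or at least one abnormal value, grows with the time observed and the number of visits. The Appendix 5 rule gives the early-start group two rounds of treatment and AE collection and the delayed-start group one. If both groups are then described by the percentage of subjects affected, ordinary background events will look more frequent after early start even if the drug does nothing. A pooled elenbecestat percentage mixes the two windows and refers to no defined length of exposure.

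Long-term safety and tolerability is the Extension's primary objective, and the safety variables are its primary endpoint. These descriptive tables are therefore the Extension's main result.

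**Working it through.** **Reproducing the stated durations.** Extension: 24 + 1 = 25 months, as stated in the synopsis. Core: 2 + 24 + 3 = 29 months, as stated in section 9.1. The protocol gives no figure for the length of a safety window, so it has to be built from these parts.

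**Windows for a subject who completes both phases.**

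| | Early start | Delayed start |
|---|---|---|
| New-AE collection | (24 + 1) + (24 + 1) = 50 months | 24 + 1 = 25 months |
| Calendar span | 24 + 3 + 24 + 1 = 52 months (52.9 with the full 4-week gap) | 25 months |
| Planned time on drug | 48 months | 24 months |
| Scheduled on-treatment laboratory draws | 11 (Table 5, Visits 3-13) + 9 (Table 9, Visits 16-24) = 20 | 9 |

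Counting visit days instead of nominal months (757 days to 4 weeks after the last dose in each phase) gives 49.7 and 24.9 months.

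**Effect of window length alone.** Assume the same constant hazard in both groups and no drug effect. If the risk over 25 months is r, the risk over 50 months is 1 - (1 - r)^(50/25) = 1 - (1 - r)^2.

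| 25-month risk | 50-month risk | Ratio |
|---|---|---|
| 1% | 2.0% | 1.99 |
| 5% | 9.8% | 1.95 |
| 10% | 19.0% | 1.90 |
| 20% | 36.0% | 1.80 |
| 40% | 64.0% | 1.60 |

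**The same example per subject-time.** For r = 10% the hazard is -ln(0.90)/25 per month, or 5.06 first events per 100 subject-years at risk, equal in both groups. Dividing affected subjects by total exposure, without stopping the clock at the first event, removes most of the gap but not all of it: 10/(25/12) = 4.80 against 19/(50/12) = 4.56 per 100 subject-years. That is a reason to match periods as well as to use a time denominator.

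**If the Core Safety Analysis Set is used literally.** Early discontinuers then stay in the early-start group. Assume a share d stops drug at 12 months on average (13 months of AE collection) and all others enter and complete the Extension. The mean window is 50(1 - d) + 13d: 42.6 months at d = 20%, 38.9 at 30% and 35.2 at 40%. All exceed 25. If only a share e of the others enters, the mean is (1 - d)(25 + 25e) + 13d. It falls to 25 months only when e is as low as 12% (d = 20%), 21% (d = 30%) or 32% (d = 40%).

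**The case against.** The baseline rule is defensible. It gives every subject a reference value taken before the first elenbecestat dose, which is what a change from baseline in laboratory values, ECG, vital signs or MRI needs. Long-term dosing is the stated target, so cumulative experience from first dose is a natural thing to describe. By-visit summaries do not grow with the window. The output is descriptive, and exposure-adjusted rates may be set out in a statistical analysis plan that was not at hand. Appendix 5 also speaks of a baseline, not a counting window; the window follows only through the TEAE and abnormality definitions.

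Much of this stands, and it confines the point to crude incidences. It does not remove it: the protocol itself fixes both the arm-specific baseline and, through its reference to the Core methods, the crude percentage.

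Two stronger readings are tempting and are not supported.

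- A reader might infer that the early-start group contains only subjects who tolerated 24 months of drug, so that AEs leading to discontinuation in that period are zero by construction. That follows from the eligibility rule only if the analysis is limited to Extension entrants. Appendix 5 also applies the Core Safety Analysis Set, and its baseline sentence does not require Extension entry of subjects randomised to elenbecestat. The text does not settle the matter. Delayed-start subjects are selected too, as completers of 24 months on placebo.
- A reader might infer a contradiction with section 9.1, which says: "For all subjects, assessments performed at Visit 15 will serve as baseline values for the Extension Phase". That sentence defines the Extension baseline; Appendix 5 says which group uses it for safety. The two can both be true, and Appendix 5 elsewhere uses the Core baseline for Extension efficacy and biomarkers.

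**Conclusion.** The point holds for incidence summaries. For subjects who complete both phases, AE collection runs to about 50 months after early start and 25 after delayed start. Window length alone then inflates the early-start percentage by a factor between 1.99 (1% risk) and 1.60 (40% risk). Approximately twice is right only for uncommon events. The windows follow from the protocol's own periods; the factors rest on an assumed constant hazard, full follow-up in both groups and no drug effect.

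If early discontinuers are kept in, the mean early-start window is about 35 to 43 months under assumed discontinuation of 20% to 40% with all others entering. The imbalance is smaller but remains. Which population applies needs to be stated.

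The material does not support dropping the pre-elenbecestat baseline. Using Visit 15 as baseline for early-start subjects would absorb any change that persisted from 24 months of treatment.

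**What to change.** Amend the safety paragraph of Appendix 5 and its copy in the synopsis as follows.

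- Keep the pre-elenbecestat baseline for change-from-baseline and shift summaries.
- Report AE and abnormality incidences as events or subjects per subject-time, using the subject-months planned in section 9.7.1.8.1, by time since first elenbecestat dose in matched periods of 0-24 months and more than 24 months. The later period has early-start subjects only and is descriptive of long exposure, not a comparison.
- Leave the off-drug interval between the phases out of exposure, and treat events in it consistently with that.
- For months 0-24 of early start, use all Core elenbecestat subjects in the Safety Analysis Set, not only those who enter the Extension. State the Extension safety population explicitly.
- Optionally add an Extension-only AE table counting events after the first Extension dose in both groups.
- State that crude percentages over unequal windows are not to be compared or pooled.

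The cost is a wording change and a few extra tables. No new data, visits or subjects are needed.

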
Pooling of study 301 and 302 analysis, with decreased subjects and sites in each study
	
Sample size re-estimation indicated the requirement for 1900 subjects compared with the original 1330 subjects per study. Studies will be combined to achieve the required numbers.
	
Synopsis
 
 • Site(s) • Core Study Objectives • Study Design • Number of Subjects • Statistical Methods 
Section 6 Section 8.1 Section 8.2 Section 9.1 Section 9.2.1 Section 9.3 Section 9.7.1.1 Section 9.7.2

Study 202 summary of safety
	
Emerging clinical data
	
Section 7.1

Revisions to Version 5.0

New version/date: Version 6.0/21 Jan 2019 (per Amendment 05)

Change	Rationale	Affected Protocol Sections
and efficacy added and its Extension Phase, exposure	indicating acceptable safety and signals of clinical efficacy	Section 9.4.4
Key secondary objectives defined	Three key secondary objectives have been defined from the multiple secondary objectives, indicating those of most importance that will be tested in a hierarchical manner if the primary objective is significant.	Synopsis 
 • Core Study Objectives • Statistical Methods Section 8.2 Section 9.7.1.1.2 Section 9.7.1.6.2
Added Alzheimer’s Disease Composite Score (ADCOMS) as a secondary objective for the Core Study	This novel endpoint has been included, aimed at optimizing sensitivity to disease progression over time in the MCI population, allowing earlier detection of clinical change.	Synopsis 
 • Core Study Objectives, Secondary Objectives • Assessments • Study Endpoints Section 8.2 Section 9.2.1 Section 9.2.3 Section 9.5.1.3.1 Section 9.7.1.1.2 Section 9.7.1.6.2
Added of CDR-SB and ADCOMS enriched by baseline amyloid PET SUVR as a secondary objective for the Core Study	Elenbecestat may be more effective when amyloid reaches a minimum level but before too much is on board	Synopsis 
 • Core Study Objectives, • Study Endpoints Section 8.2 Section 9.7.1.1.2 Section 9.7.1.6.2
Added a biomarker objective and endpoints for the Core Study	Clarification	Synopsis 
 • Core Study Objectives • Biomarker Endpoints • Analyses for Biomarker Endpoints Section 8.2 Section 9.7.1.1.3 Section 9.7.1.7.3
Revised country list	To reflect that South Africa is a participating country	Synopsis 
 • Study Design Section 9.1
Added that if subjects have	To clarify that subjects would	Synopsis

Revisions to Version 5.0

New version/date: Version 6.0/21 Jan 2019 (per Amendment 05)

Change	Rationale	Affected Protocol Sections
non-MRI compatible devices fitted during treatment, then a computed tomography scan may be utilized to assess safety, if deemed appropriate by the investigator	not need to withdraw from study	
 • Study Design Section 9.1.2.1 Section 9.5.1.5.7
Added that CSF will be used to assess PD, PK, and exploratory biomarkers.	Clarification	Synopsis 
 • Study Design Section 9.1.2.1
Added that CSF and PET assessments should be conducted before any other visit assessments and while the subject is still study drug	Clarification	Synopsis 
 • Study Design Section 9.1.2 Section 9.1.2.1
Added that new AEs will be collected for 4 weeks post last dose and followed-up for 12 weeks, or until resolution, whichever comes first. AEs relating to study procedures will be collected until the end of study participation	Clarification	Synopsis 
 • Study Design Section 9.3.3
Historical cerebrospinal fluid (CSF) samples, if collected, processed, and stored under appropriate conditions and approved by the sponsor, may be analyzed to determine CSF amyloid positivity	Allows historical CSF sample to be analyzed to determine eligibility	Synopsis 
 • Inclusion Criteria • Assessments Section 9.3.1
Added that levels of Vitamin B12 may be confirmed with methylmalonic acid analysis, if available	For flexibility on Vitamin B12 deficiency analysis	Synopsis 
 • Exclusion Criteria Section 9.3.2 Table 3 Section 9.5.2.2 Table 6

Revisions to Version 5.0

New version/date: Version 6.0/21 Jan 2019 (per Amendment 05)

Change	Rationale	Affected Protocol Sections
Revised exclusion criterion (#14) regarding a prolonged QTc interval calculated using Fridericia's formula (QTcF) was changed to clarify that if the QTcF machine read is greater than 440 ms on the first single 12-lead ECG, 2 additional 12 lead ECGs will be performed.	Machine read QTcF values might be lower than central reads. Subjects are SF if the average of 3 ECGs on central read > 450 ms. Instructing sites to perform triplicate ECGs when machine reads are > 440 ms will ensure all required evaluations are completed.	Synopsis 
 • Exclusion Criteria Section 9.3.2 • Section 9.5.1.5.6 • Table 5
Revised exclusion criterion (#19) to clarify that subjects who participated in a clinical study that involved a new chemical entity or investigational drug for Alzheimer's Disease (AD) are to be excluded	Clarification	Synopsis 
 • Exclusion Criteria Section 9.3.2
Added events of possible abuse potential to the safety assessments for the Core Study and Extension Phase	Clarification	Synopsis 
 • Assessments Section 9.7.1.8
Revised text to clarify that if a Grade 2 or greater lymphocytopenia (less than 800/mm ³) occurs twice during the Treatment Period, that is confirmed on repeat testing and within a 6-month period, then the subject should be discontinued permanently from the study drug in the Core Study.	To clarify that this applies to Treatment Period in the Core Study.	Synopsis 
 • Assessments Section 9.3.3
Added timepoints when the NPI-10 item will be conducted in the Extension Phase	Wording added	Synopsis 
 • Assessments
Clarified that ApoE4 status may be included in the model if appropriate	Clarification	Synopsis 
 • Efficacy Analyses Section 9.7.1.6.1 • Section 9.7.1.6.2

Revisions to Version 5.0

New version/date: Version 6.0/21 Jan 2019 (per Amendment 05)

Change	Rationale	Affected Protocol Sections
Revised Core Study analysis of biomarker endpoints to clarify that change from baseline in functional magnetic resonance imaging (fMRI) parameters as appropriate, will be determined	Clarification	Synopsis 
 Analysis of Biomarker Endpoints Section 9.7.1.7.3
Added that a futility analysis is planned when approximately 30% of subjects have had an opportunity to complete the 24-month visit of the Core Study by the interim cutoff date	Clarification	Synopsis 
 Interim Analyses Section 9.7.3
Clarified that subjects who agree to take part in the Extension Phase and the substudies during the Extension Phase, will need to provide separate Extension Phase-specific written informed consent	Clarification	Section 5
Added a valid period for assessment results of Tiers 1 to 5	Clarification	Section 9.1.1.1
Added information to permanent discontinuation	Clarification to cover subjects where the study drug had been temporary suspended for more than 3 weeks	Section 9.3.3
Added that termination of therapy for symptomatic treatment of AD during the study should be undertaken in compliance with local standard of care.	Clarification	Section 9.4.7
Added information on CSF sampling at Visit 13 (early discontinuation [ED])	Clarification to avoid samples being taken when subject has been off the study drug for more than 7 days.	Section 9.5.1.3.3
Revised to clarify that postdose pharmacokinetic (PK) samples will not be needed for subjects who are temporary suspended from study drug or permanently stopped the study drug at the ED visit	To clarify requirements for collection of PK samples when subjects are not being dosed.	Section 9.5.1.4.1
Added neurogranin as an	Correction	Table 2

Revisions to Version 5.0

New version/date: Version 6.0/21 Jan 2019 (per Amendment 05)

Change	Rationale	Affected Protocol Sections
Exploratory Biomarker Subset		
Added details as to when amyloid positron emission tomography (PET) and tau PET imaging will be conducted	Clarification	Section 9.5.1.4.2
Added how adverse events (AEs) will be handled for subjects who permanently discontinue study drug, but continue in the study.	Wording added	Section 9.3.3 Section 9.5.1.5.1
Added treatment changes in depigmentation/hypopigmentation/vitiligo/loss of hair color to the list of AEs that will require the collection of information to provide detailed description of the event	AE of interest added	Section 9.5.1.5.1
Revised blood sampling for immunological assessments and added corresponding footnote	Based on Data Safety Monitoring Board recommendation	Table 5 Table 6
Revised the example of the locally approved amyloid-imaging agent to Neuraceq	To reflect main imaging agent in use during the study	Table 4 Table 5
Added a footnote to state that Visit 2 bottles of study drug will be redispensed at Visit 3	Clarification	Table 5
Added footnotes to state when initiation, termination or change in dose is permitted or that herbal medications and preparations should be discussed with the medical monitor	Clarification	Listing 4 in Section 12
Revised list of permitted medication and permitted medication if used for short-term basis	Clarification	Listing 5 in Section 12
Added footnote that herbal medications or preparations should be discussed with the medical monitor and benzodiazepines were deleted	Clarification	Listing 5 and Listing 6 in Section 12

Revisions to Version 5.0

New version/date: Version 6.0/21 Jan 2019 (per Amendment 05)

Change	Rationale	Affected Protocol Sections
An editorial revision was made to remove “(E2609)”; grammatical, typographical, and formatting changes were also made	Correction	Throughout

Revisions to Version 4.0

New version/date: Version 5.0/19 Jul 2018 (per Amendment 04)

Change	Rationale	Affected Protocol Sections

Addition of optional tau PET longitudinal substudy for study-eligible subjects from select geographical sites in the US (based on the proximity to the tau PET ligand manufacturing sites) who have an amyloid positive study-specific PET scan and consent to participate in the optional amyloid PET longitudinal substudy. Tau PET scanning will be performed using a sponsor-supplied tau PET imaging agent, eg PI-2620.
	
To allow for longitudinal assessment of brain tau pathology by tau PET in a substudy. Abnormal aggregation of tau in the brain is a factor in many neurodegenerative diseases, including Alzheimer’s disease.
	
Synopsis
 
 • Objectives • Study Design • Assessments • Statistical Methods 
Section 5.3 Section 8.2 Figure 1 Section 9.1 Section 9.1.1 Section 9.1.1.1 Section 9.1.1.1.5 Section 9.1.2 Section 9.1.2.1 Section 9.2.4 Section 9.5.1.4.2 Table 4 Table 5 Section 9.7.1.1.3 Section 9.7.1.7.3

Revisions to Version 3.0

New version/date: Version 4.0/28 Jun 2017 (per Amendment 03)

Change	Rationale	Affected Protocol Sections
Added that the start of the open-label Extension Phase will require prior approval of an amendment from applicable Health Authorities	Added for consistency with Section 9.1.3.	Synopsis 
 Study Design
Specified duration of the Prerandomization Phase and that randomization should occur no more than 10 days after completion of all screening assessments/procedures and confirmation of eligibility	Added for clarification	Synopsis 
 Conduct of the Study Section 9.1.1 Section 9.1.2 Section 9.5.2.1 (Table 5)
Added that for any given subject, every effort should be made to ensure that the diagnosing clinician (responsible for the initial diagnosis and for disease staging) and the Clinical Dementia Rating (CDR) rater remain unchanged throughout the study.	Added to maximize consistency in diagnosis, disease staging and rating of the CDR.	Synopsis 
 Conduct of the Study Section 9.1.1.1.1 Section 9.1.2.1 Section 9.5.1.3.1 Section 9.5.2.1 (Table 4 and Table 5)
Removed pharmacodynamic (PD) blood specimen collection from the Screening Period and stipulated that Baseline blood draws for PD assessment will be performed predose at Visit 2 (Randomization Phase) rather than during Screening.	Revised for clarification	Synopsis 
 Conduct of the Study Pharmacodynamic, Pharmacogenomic, and Other Biomarker Assessments Section 9.1.2 Section 9.1.2.1 Section 9.5.1.4.2 Section 9.5.2.1 (Table 5)
Specified that safety assessments of immune status will be performed throughout the study	Revised for clarification	Synopsis Conduct of the Study
Specified that the MMSE and CDR requirements are to be met at Screening	Revised for clarification	Synopsis 
 Inclusion Criteria Section 9.3.1
Listed cerebrospinal fluid (CSF) amyloid beta (A β) (1-42) and	Revised for clarification, since CSF assessment of brain	Synopsis 
 Conduct of the Study

Revisions to Version 3.0

New version/date: Version 4.0/28 Jun 2017 (per Amendment 03)

Change	Rationale	Affected Protocol Sections

tau:Aβ (1-42) ratio as examples of Alzheimer’s disease (AD) biomarkers for brain amyloid pathology.
	
amyloid pathology will also include other biomarkers
	
 • Inclusion Criteria • Pharmacodynamic, Pharmacogenomic, and Other Biomarker Assessments • Bioanalytical Methods 
Section 9.1.1.1 Section 9.1.1.1.5 Section 9.1.2 Section 9.1.2.1 Section 9.2.4 Section 9.3.1


Added that positron emission tomography (PET) scans performed at the Early Discontinuation (ED) Visit should only be performed if 6 months has elapsed since the prior PET scan.
	
Added to define a minimal interval between PET scans for the PET longitudinal substudy.
	
Synopsis
 
 • Conduct of the Study • Pharmacodynamic, Pharmacogenomic, and Other Biomarker Assessments 
Section 9.1.2 Section 9.1.2.1 Section 9.5.1.4.2 Section 9.5.2.1 (Table 5)

Specified that historical PET scans must have been positive for amyloid in order to be considered for eligibility purposes
	
Added for clarification
	
Synopsis
 
 • Inclusion Criteria • Pharmacodynamic, Pharmacogenomic, and Other Biomarker Assessments 
Section 9.3.1

Added that subjects must have the capacity to provide informed consent (as determined in accordance with applicable professional standards and local laws/regulations) to enroll in the study.
	
Added for clarification based upon feedback from Health Authority(ies)
	
Synopsis
 
 • Inclusion Criteria 
Section 9.3.1

Added that the study partner must be literate.
	
Added for clarification
	
Synopsis
 
 • Inclusion criteria

Revisions to Version 3.0

New version/date: Version 4.0/28 Jun 2017 (per Amendment 03)

Change	Rationale	Affected Protocol Sections
		Section 9.3.1
Specified that findings of “diffuse” white matter disease “as defined by a score of 3 on the age-related white matter changes score (Wahlund, et al., 2001)” on “central read” brain MRI findings at Screening are exclusionary. Clarified that evidence of multiple lacunar infarcts is exclusionary, regardless of region, whereas evidence of stroke is exclusionary when it involves a major vascular territory.	Added for clarification	Synopsis 
 Exclusion criteria Section 9.3.2 Section 10
Provided guidance for possible inclusion of subjects successfully treated for hepatitis C.	Added for clarification	Synopsis 
 Exclusion criteria Section 9.3.2
Specified that history of ophthalmic shingles or history of ocular herpes simplex virus infection are exclusionary, in addition to active infections of ophthalmic shingles or ocular herpes simplex virus.	Added for clarification	Synopsis 
 Exclusion criteria Section 9.3.2
Removed “ocular” inflammatory disease requiring immunosuppressive or immunomodulatory therapy from exclusion criteria	Ocular therapy is permitted.	Synopsis 
 Exclusion criteria Concomitant Drug/Therapy Section 9.3.2 Section 9.4.7 Listing 2 of Appendix 2
Removed exclusion for significant abnormalities in laboratory tests or electrocardiogram (ECG) at Baseline assessment	Results from Baseline assessment will not be available at the Baseline Visit	Synopsis 
 Exclusion Criteria Section 9.3.2
Clarified that the exclusion of subjects with a prolonged QTcF interval is based on the central read of the Screening ECG.	Added for clarification	Synopsis 
 Exclusion Criteria Section 9.3.2

Revisions to Version 3.0

New version/date: Version 4.0/28 Jun 2017 (per Amendment 03)

Change	Rationale	Affected Protocol Sections
Specified that “short-term” concomitant use of benzodiazepines is permitted as specified in the protocol	Added for clarification	Synopsis 
 Concomitant Drug/Therapy Section 9.4.7 Listings 5 and 6 of Appendix 2
Specified that repeat testing for subjects who develop Grade 2 or greater lymphocytopenia should be performed as soon as possible, with the repeat blood sample drawn no later than 5 calendar days from the date of the original test result.	Added for clarification	Synopsis 
 Safety Assessments Section 9.3.3
Updated text describing monitoring adverse events (AEs) that may signal drug abuse potential, physical withdrawal or dependence; specified that monitoring will include the Treatment Period and the first 4 weeks of the Follow-up Period	Added for clarification and alignment with current US Food and Drug Administration (FDA) Guidance for Industry for “Assessment for Abuse Potential for Drugs”	Synopsis 
 Safety Assessments Section 9.5.1.5.1 Section 9.5.2 (Table 5) Section 9.5.4.3.1 Section 10 Appendix 3
